Appendix E: Magnetic Resonance Imaging Procedures

Background

MRI will be performed to accomplish several objectives, including:

- determination of eligibility for study participation
- identification of the target site for AST-OPC1 injection
- evaluation of the injection site for safety
- evaluation of distant regions of the CNS for safety
- acquisition of data for possible research analyses

The imaging protocol for the clinical safety evaluation was designed with consideration given to the results of the nonclinical biodistribution studies of AST-OPC1 following injection into the cervical spinal cord as described in Section 1.2.4.

Based on these data, all MRI exams will include imaging of the cervical spine. Sagittal views of the cervical spine will include a field of view that extends from the top of the cerebellum to the upper thoracic spine (approximately T1-T2 level). Selected MRI exams (baseline, Day 365) will also include imaging of the brain. All MRI exams will include imaging with and without gadolinium-DTPA contrast to detect, evaluate, and monitor any potentially enlarging abnormal cysts or masses.

Standard Imaging Parameters

All MR imaging should be performed on systems with a static magnetic field strength of at least 1.5 Tesla in order to ensure that high-resolution images with good signal-to-noise can be obtained. All MR images of the spine should be obtained with a phased array receive coil (or equivalent) for the same reason as above.

Suggested imaging sequences for spine MRI include:

- Sagittal T1-weighted spin-echo and T2-weighted fast spin-echo
 - field of view: top of cerebellum to upper thoracic spine (approx. T1-T2)
 - slice thickness: 3 mm + 0.3 mm gap between slices
 - T1 scans: TR/TE/nex: 600/20/2
 - o T2 scans: TR/TE/ETL/nex: 2000-3000/80-100/4-8/2-4
 - recommendations to minimize artifacts due metallic implants: turn off fat suppression and increase receiver bandwidth to maximum allowed by the system

- Axial T1-weighted spin-echo and T2-weighted fast spin-echo
 - \circ $\;$ Number of slices: 16, with middle slices at the level of the injury epicenter $\;$
 - Slice thickness: 4 mm + 1 mm gap between slices
 - T1 scans: TR/TE/nex: 600/20/2
 - o T2 scans: TR/TE/ETL/nex: 2000-3000/80-100/4-8/2-4
 - Recommendations to minimize artifacts due metallic implants: turn off fat suppression and increase receiver bandwidth to maximum allowed by the system

All MRI exams will include postcontrast (gadolinium-DTPA) T1-weighted images in the sagittal and axial planes with the same parameters used for the respective pre-contrast images (unless the subject is allergic to contrast).

Suggested MRI scans of the brain include routine T1-weighted and T2-weighted scans in the sagittal and axial planes, plus postcontrast T1-weighted images.

Central Reading of MRI Scans

All study-driven MRI reading will be performed by a central group of neuroradiologists with extensive experience in MRI evaluation of spinal cord trauma. The images will be sent to the central group electronically via an imaging contract research organization.

The poststabilization screening/baseline MRI scan will be used to determine the whether the following eligibility criteria are met:

- single spinal cord lesion on a post-stabilization magnetic resonance imaging (MRI) scan, with sufficient visualization of the spinal cord injury epicenter and lesion margins to enable post-injection safety monitoring
- absence of anatomical transection or significant laceration
- spinal cord lesion with anteroposterior diameter of the spinal cord ≥ 2 mm at point of maximal compression on a midline sagittal image from a poststabilization MRI

The screening/baseline MRI will also be used to make a preliminary determination of the target site for AST-OPC1 injection. This site should be near the caudal margin of the injury epicenter, and within damaged, but nonhemorrhagic tissue.

Several additional parameters may be measured for future research analyses. These may include:

- Length of contusion (ie, maximal extent of petechial hemorrhages)
- Presence/absence of intramedullary hemorrhage
- Length of intramedullary hemorrhage

- Length of edema
- Percent compression at epicenter

Following AST-OPC1 injection, the MR images will be assessed according to standard practice and with specific attention to the following potential risks:

- intramedullary hemorrhage, CSF leak, epidural abscess, infection
- evidence of expanding cyst or mass at the injection site or elsewhere in CNS
- evidence of inflammatory lesion(s) at injection site or elsewhere in CNS
- evidence of CSF flow obstruction

1. LIST OF ABBREVIATIONS AND ACRONYMS

Abbreviations and Acronyms	Description
AE	Adverse Event
AIS	ASIA Impairment Scale
ASIA	American Spinal Injury Association
BMI	Body Mass Index
CDISC	Clinical Data Interchange Standards Consortium
CDMS	Clinical Data Management System
CFB	Change From Baseline
CNS	Central Nervous System
CSR	Clinical Study Report
CSF	Cerebrospinal Fluid
DMC	Data Monitoring Committee
DPC	DP Clinical, Inc.
DVT	Deep Vein Thrombosis
ECG	Electrocardiogram
eCRF	Electronic Case Report Form
GRASSP	Graded Redefined Assessment of Strength, Sensibility and Prehension
HBV	Hepatitis B Virus
HCV	Hepatitis C Virus
HIV	Human Immunodeficiency Virus
HLA	Human Leukocyte Antigen
ICH	International Conference on Harmonisation of Technical Requirements for Registration of Pharmaceuticals for Human Use
ISNCSCI	International Standards for Neurological Classification of Spinal Cord Injury
kg	kilogram
MedDRA	Medical Dictionary for Regulatory Activities
mg	milligram
ml	Milliliter
MRI	Magnetic Resonance Imaging
NLI	Neurological Level of Injury

Abbreviations and Acronyms	Description
ODS	Output Delivery System
PCFB	Percent Change From Baseline
PT	Preferred Term
QC	Quality Control
RTF	Rich Text File
SAE	Serious Adverse Event
SAP	Statistical Analysis Plan
SAS	Statistical Analysis System
SCI	Spinal Cord Injury
SCIM	Spinal Cord Independence Measure
SD	Standard Deviation
SEM	Standard Error of the Mean
SOC	System Organ Class
SOP	Standard Operating Procedure
SPD	Syringe Positioning Device
TEAE	Treatment- Emergent Adverse Events
TLF	Tables, Listings, and Figures
UEMS	Upper Extremity Motor Score
WHODrug	World Health Organization Drug Dictionary
ZPP	Zone of Partial Preservation

2. INTRODUCTION

The purpose of this statistical analysis plan (SAP) is to document a more technical and detailed elaboration of the principal features stated in the protocol. This plan includes detail procedure for executing the efficacy analysis for the primary and secondary efficacy endpoints. Further analysis of safety variables (adverse events, clinical laboratory tests, vital signs, AST-OPC1 injection and MRI results) are described in greater detail in this document. Finally, the SAP will reasonably ensure that the tables which will be produced from these analyses, and the data listings, figures, and statistical methodologies that will be used, are complete and allow for the arrival of valid conclusions regarding the study objectives. In the development of this SAP, the following documents and International Conference on Harmonisation of Technical Requirements for Registration of Pharmaceuticals for Human Use (ICH) guidelines were used:

- Protocol AST-OPC1-01, Amendment 3, 07 July 2017
- Electronic Case Report Form (eCRF) Casebook (31 Jul 2017)
- International Conference on Harmonisation (ICH) E3 (1995): Structure and Content of Clinical Study Reports (CSR)
- ICH E6 (R2) (2016): Guideline for Good Clinical Practice
- ICH E9 (1998): Statistical Principles for Clinical Trials

In the event that a discrepancy is found between the descriptions in the statistical section of the protocol and this document, the description in this document supersedes the descriptions in the statistical section of the protocol.

The DP Clinical, Inc. (DPC) Biostatistician is responsible for updating the SAP throughout the life of the study as needed. The responsible party at Asterias will be required to review and approve all versions of the SAP.

3. STUDY OVERVIEW

AST-OPC1-01 is an open-label, dose escalation, cross-sequential, multicenter Phase 1/2a study.

3.1 Study Objectives

3.1.1 Primary Objectives

[figure not shown]
The primary objective of this study is to evaluate the safety of 3 sequential escalating doses of AST-OPC1 administered at a single time-point between 21 and 42 days post-injury, inclusive, to subjects with subacute cervical spinal cord injuries (SCI).

3.1.2 Secondary Objectives

The secondary objective is to evaluate changes in neurological function following administration of AST-OPC1.

3.2 Study Design

AST-OPC1-01 is an open-label, dose escalation, cross-sequential, multicenter Phase 1/2a study. Subjects with cervical AIS-A SCI will receive 1 of 3 sequential dose levels (2 x 10⁶, 1 x 10⁷ or 2 x 10⁷) of AST-OPC1 injected directly into the spinal lesion within 21 and 42 days after the original injury. Subjects with cervical AIS-B SCI will receive 1 x 10⁷, or 2 x 10⁷ AST-OPC1 cells. All subjects will also receive low-dose tacrolimus for 60 days following injection to prevent immunological rejection. Subjects will be followed for safety and neurologic function for 1 year under this protocol and will then be required to participate in a companion long-term safety follow-up protocol for 14 years. In addition, eligible subjects who were enrolled and had pharmacological deep vein thrombosis (DVT) prophylaxis withdrawn in preparation for surgery, but who never received the AST-OPC1, will be followed for safety for 30 days and assessed separately. All adverse events (AE) will be monitored in an ongoing fashion by the Sponsor's medical monitor and by an independent Data Monitoring Committee.

Page 9 of 33 Confidential

Enrollment in Cohort 1 will be staggered such that there are at least 10 days between administrations of AST-OPC1 to each subject. Enrollment within Cohorts 2-5 will be staggered after the initial subject in each cohort is dosed, with at least 8 days between administration of AST-OPC1 to the first and second subjects. If the first two subjects are successfully dosed with no serious adverse events (SAE) that would trigger study suspension (per the study Suspension Rules), then the remaining subjects in that cohort may be dosed without further staggering.

An additional staggering rule for Cohorts 2-5 is that a minimum of 14 days must elapse between the dosing of any two consecutive subjects who both have a C4 neurological level of injury (NLI). This 14-day stagger for consecutive C4 NLI subjects applies throughout each of these cohorts and also would supersede the 8-day stagger noted above if the first two subjects in any cohort both have a C4 NLI.

Enrollment in Cohort 2 may commence after all three subjects in Cohort 1 have completed 30 days of follow up after AST-OPC1 administration and the safety data for Cohort 1 have been reviewed by the Data Monitoring Committee (DMC).

Enrollment in Cohort 3 may commence after at least five subjects in Cohort 2 have completed 30 days of follow up after AST-OPC1 administration and the safety data from Cohorts 1 and 2 have been reviewed by the DMC.

Enrollment in Cohort 4 may commence after at least two subjects in Cohort 2 have completed 30 days of follow up after AST-OPC1 administration and if there are no SAEs that would trigger study suspension.

Enrollment in Cohort 5 may commence after at least two subjects in Cohort 3 and at least five subjects in Cohort 4 have completed 30 days of follow up after AST-OPC1 administration and if there are no SAEs that would trigger study suspension.

For the planned DMC reviews noted above, the DMC will recommend whether enrollment of the next dose cohort can commence or whether additional follow up of the current cohort is needed prior to commencing enrollment in the next cohort.

The rationale for the 8-day stagger is that nearly all of the potential surgical complications, if they occur, will become clinically evident within the first few days after surgery. Thus, any serious complications (i.e., SAEs) would be evident within the first few days after surgery and would be reported within 24 hours of their occurrence (as required for all SAEs).

In addition, subjects in this study will receive a complete neurological exam and magnetic resonance imaging (MRI) scan for safety monitoring at 7 days after AST-OPC1 injection. The study suspension rules include several rules that could be triggered by potential complications of the AST-OPC1 injection procedure, such as: death or unexpected neurological deterioration, evidence of direct spinal cord damage related to the volume of injection, or any cerebrospinal fluid (CSF) infection or inflammation that is more than a transient reaction to AST-OPC1 injection.

On Injection Day subjects will receive the dose of AST-OPC1 as determined by cohort assignment (Table 1). AST-OPC1 may only be administered by a licensed surgeon who has both training and experience in performing intradural surgical procedures on the spine. In addition, each surgeon must be trained and qualified by the Sponsor on the use of the Syringe Positioning Device (SPD) and the injection procedure prior to their first administration of AST-OPC1.

Table 1: AST-OPC1 Dose Cohorts and Injection Preparation

Cohort	Dose (# of cells)	Concentration (cells/µL)	Volume per Injection (µL)	Number of Injections	Total Volume Administered (µL)
1	2 x 10 ⁶	4 x 10 ⁴	50	1	50
2	1 x 10 ⁷	2 x 10 ⁵	50	1	50
3	2 x 10 ⁷	2 x 10 ⁵	50	2	100
4	1 x 10 ⁷	2 x 10 ⁵	50	1	50
5	2 x 10 ⁷	2 x 10 ⁵	50	2	100

Between 6 and 12 hours after the AST-OPC1 dose, subjects will commence a course of the immunosuppressant tacrolimus, given orally at a starting dose of 0.03 mg/kg/day (divided into 2 daily doses) Days 1 through 46, tapered by 50% between Days 47 and 52 (rounding to the nearest 0.5 mg), tapered by another 50% on Day 53, and discontinued after 60 days.

If a subject is unable to take oral medication, tacrolimus may be given intravenously at a dose of 0.01 mg/kg/day as a continuous infusion, switching over to oral medication as soon as practicable. During intravenous infusion of tacrolimus, standard monitoring for acute anaphylaxis will be observed in accordance with approved labeling. Subjects will not be allowed to eat any grapefruit-containing food items through 60 days as this may alter the pharmacokinetics of tacrolimus.

Blood samples will be taken for monitoring blood levels of tacrolimus (immediately prior to the first daily dose if given orally) twice per week starting on Study Day 4 (+/- 1 day) and continuing for 30 days decreasing to once per week for 60 days (or through termination of tacrolimus) (see Section 7 of the protocol). Dosing of tacrolimus will be adjusted in order to maintain blood levels between 3 and 7 ng/mL. Additional monitoring of blood chemistry for possible tacrolimus toxicity will be as outlined in Section 7 of the protocol.

Tacrolimus dosing may be decreased or discontinued for unacceptable toxicity at the investigator's discretion; this might include infection or uncontrolled fever, liver function test elevation, creatinine elevation, seizure, or thrombotic thrombocytopenic purpura.

Subjects will receive a single administration of AST-OPC1. Subjects will be followed for 1 year post-injection of AST-OPC1 under this protocol and for an additional 14 years under a

companion long term follow-up protocol. Subjects must agree to and sign the informed consent for long-term follow-up in order to participate in this study.

All required tests and observations with their schedules are summarized in Section 3.2.2.

3.2.1 Sample Size Considerations

A total of 23-35 subjects were planned to receive AST-OPC1. Enrollment concluded on December 15, 2017 and a total of 25 subjects were enrolled and received AST-OPC1 across the five cohorts:

- Cohort 1: 3 Subjects
- Cohort 2: 6 Subjects
- Cohort 3: 6 Subjects
- Cohort 4: 6 Subjects
- Cohort 5: 4 Subjects

The sample size is based on the study design considerations for a Phase 1/2a study. This trial employs a cross-sequential cohort design for Phase 1 dose escalation in cervical AIS-A and AIS-B subjects. Power calculations have not been performed, as the primary objective is to collect safety and tolerability information on a limited number of subjects per dose level and AIS Grade, and an effect size cannot yet be estimated.

3.2.2 Study Assessments Schedules

Study assessments are described in detail in the protocol, and summarized below in Table 2.

Table 2: Summary of Study Procedures

Part A:

	Screen	Baseline	Surgery	Po	st-Injectio	on
	Days -11 to -3	Days –2 to – 1	Injection Day	Days 1-6	Day 7	Days 8-29
Procedure					(+/- 1 day)	
Demographic data	х					
Past and current medical history	х					
Complete physical exam	х					
Brief physical exam		х		Day 1	х	
Vital signs	х	X ³	Х	Daily	х	
Neurological exam		X 5			х	
ISNCSCI exam	х	X 1			х	
GRASSP		X 5				
SCIM		X ⁵				
MRI ²	Day -7 to -3				х	
ECG	х				х	
Hematology	х	х		Day 1	х	
Blood chemistry	х	х		Daily	х	2/week
Serology for HIV, HBV, HCV	x					
Panel reactive antibodies	X					
Pregnancy test, if applicable	X					
48-hour blood culture	Day –3					
Fasting blood glucose		X ⁴				
Blood for HLA typing		X 5				
Blood for immune response monitoring		X ⁵			Х	
Blood for xenotransplantation archival		X 5				
Withhold DVT prophylaxis		Day -1				
CSF via lumbar puncture			Х			
Begin tacrolimus			Х			
Restart DVT prophylaxis				Day 1		
Tacrolimus blood levels				Day 3 ⁶	Х	2/week
Concomitant medications				I	1	\rightarrow
Adverse events						\longrightarrow

Part B:

	Day 30	Days 31-59	Day 60	Day 90	Day 180	Day 270	Day 365
Procedure	(+/- 3 days)		(+/- 7 days)	(+/- 7 days)	(+/- 14 days)	(+/- 14 days)	(+/- 14 days)
Complete physical exam							х
Brief physical exam	Х		х	х	Х		
Vital signs	Х		х	х	Х		Х
Neurological exam	Х		х	х	Х		Х
ISNCSCI exam	Х		х	х	Х	х	Х
GRASSP				х	Х	х	Х
SCIM questionnaire	Х		х	х	Х	х	Х
Pain questionnaire	Х			х	Х		Х
Bowel/Bladder questionnaire	Х				Х		х
MRI ²	Х				Х		Х
Hematology	Х		Х	х	Х		Х
Blood chemistry	Х	1/week	х	х	Х		Х
Fasting blood glucose	Х						
Blood for immune response monitoring	х		х	х	х		х
Tacrolimus blood level	Х	1/week	х				
CSF via lumbar puncture			х				
Blood for xenotransplantation archival	х						х
Concomitant medications							\rightarrow
Adverse events							\longrightarrow

Footnotes for Table 2, Parts A and B

- ISNCSCI exam (may be performed on Day -3 to -1, unless the screening ISNCSCI was performed on Day -3)
- 2 MRI of cervical spine and brain at Screen & 1 Year; MRI of cervical spine only at Days 8, 31, 181
- Witals on day -2 and -1
- 4 May be done pre-op on Injection Day
- May be performed as early as Day -4 if required to accommodate clinical site staff availability
- 6 Tacrolimus blood level on Day 4 may be obtained +/- 1 day

4. STUDY ENDPOINTS AND DEFINITIONS

4.1 Primary Endpoints

The primary endpoint of this Phase 1/2a study is safety and includes observations related to AST-OPC1 cells, the injection procedure, and the protocol-specified immunosuppression regimen. They include:

- Incidence, severity and relatedness of adverse events
- Changes in laboratory variables
- Changes at the injection site as monitored by MRI

Definitions relating to AEs and serious adverse events (SAE) are given in Section 10 of the protocol.

4.2 Secondary Endpoints

The secondary endpoints are changes in neurological function as measured on the International Standards for Neurological Classification of Spinal Cord Injury (ISNCSCI) examinations 30, 60, 90, 180, 270 and 365 days after AST-OPC1 injection. The endpoints will include:

- Upper Extremity Motor Scores (UEMS) sum of motor score from C5 to T1
- Motor Level defined by the lowest key muscle function that has a grade of at least 3 (on supine testing), providing the key muscle function represented by segments above that level are judged to be intact (graded as 5).

4.3 Exploratory Endpoints

Potential improvements in arm/hand function, self-care ability, and overall volitional ability will be evaluated by changes from baseline on the following endpoints:

- Graded and Redefined Assessment of Strength, Sensibility, and Prehension (GRASSP) is a quantitative measure of upper limb function in cervical SCI
- Spinal Cord Independence Measure (SCIM), particularly the SCIM self-care subscale, assesses the recovery of the ability of individuals with SCI to perform basic everyday tasks
- Changes in lower urinary tract and bowel function as assessed by the respective International Spinal Cord Injury Basic Data Set questionnaires
- Changes in post-treatment neuropathic pain as assessed by the International Spinal Cord Injury Pain Basic Data Set with regard to neuropathic pain.

4.4 Definitions

4.4.1 Study Day and Study Reference Period

Time will be measured as Study Day defined according to Clinical Data Interchange Standards Consortium (CDISC) standard. That is, the date of the AST-OPC1 injection is Study Day 0. The date before the AST-OPC1 injection is Study Day -1. Study day can be calculated as follows:

Study Day = visit date – date of AST-OPC1 injection

Last study day for a subject is the subject's last clinical visit date recorded on the subject status eCRF. If this date is missing for a subject, the last date found in the clinical database (e.g., clinical lab test date or date of vital sign collection) will be used as the last study date for the subject.

Total days on study are the total number of days a subject has been followed up after AST-OPC1 injection. Mathematically it can be calculated as follows:

Total days on study = last study date - date of AST-OPC1 injection + 1

4.4.2 Baseline and Change from Baseline

Unless indicated otherwise, change from baseline (CFB) will be calculated as follows, where the baseline assessment is the last assessment before AST-OPC1 injection:

• CFB = Value at Visit - Baseline

Percent change from baseline (PCFB) will be calculated as follow:

• PCFB (%) = 100*(Value at Visit - Baseline)/Baseline

5. STATISTICAL ANALYSIS GENERAL CONSIDERATIONS

5.1 Analysis Populations

Screened Population

The Screened Population will include all subjects who completed an informed consent form. This will be used for the purposes of summarizing disposition.

All Treated Population

The All Treated Population will include all subjects who received an injection of AST-OPC1. This will be used for all safety analyses.

Intent to Treat Population

The Intent to Treat Population will include all subjects who received an injection of AST-OPC1 in Cohorts 2 through 5. This population will be used for all efficacy analyses, and results will be presented for the overall, aggregated population.

Not Treated Population

The Not Treated Safety Population will include all subjects who have pharmacological deep vein thrombosis prophylaxis withdrawn in preparation for the surgery, but do not receive AST-OPC1. This population will have safety data collected for 30 days.

A topline summary of Adverse Events will be presented for the Not Treated Population, and no further data summaries will be presented for this population. The Not Treated Population will have the data listed with the Screen Failure subjects, separately from the All Treated Population.

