9 PLANNED ANALYSES

All analyses will be descriptive in nature. No inferential statistical tests will be conducted.

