9.3 Data Analysis Methods

For all safety and efficacy analyses, the All Treated population will be used, comprised of all subjects who received an injection of AST-OPC1. The 30-day safety data from subjects who had their DVT prophylaxis withdrawn but who never received AST-OPC1 will be assessed separately.

Conventional descriptive statistics will be used to summarize subject demography, baseline characteristics, disposition, and history. Discrete variables will be expressed with number and percentage and continuous variables with mean, standard deviation, median, and range as appropriate. Due to the small sample sizes per dose level and AIS grade planned for this study, data tabulations may be supplemented with subject narratives.

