9.3.2 Efficacy Analyses

Neurological function will be evaluated by characterizing upper extremity motor scores and motor level on the ISNCSCI exam (point estimate and 95% CI) by time point. The percentage of AIS-A subjects within Cohorts 2 and 3 who recover at least 2 motor levels at 180 days and at 365 days will be evaluated and compared to recent historical controls (Steeves, 2011 & 2012).

The results from the exploratory assessment tools (GRASSP, SCIM, Spinal Cord Ability Ruler, urinary tract and bowel function) will be tabulated and analyzed using statistical methods appropriate for each type of data set. Efficacy results will be presented by dose level and AIS grade, and across all subjects as appropriate.

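### The SAP pools Cohorts 2–5 in every ISNCSCI, SCIM and GRASSP table, so the AIS-A responder percentage and the dose and AIS-grade split planned in protocol 9.3.2 appear nowhere

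*SAP*

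**What the plan says.** **Protocol.** Section 9.3 sets the population: "For all safety and efficacy analyses, the All Treated population will be used". Section 9.3.2 then asks for three things:

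- "upper extremity motor scores and motor level on the ISNCSCI exam (point estimate and 95% CI) by time point";
- a responder analysis, "The percentage of AIS-A subjects within Cohorts 2 and 3 who recover at least 2 motor levels at 180 days and at 365 days", compared with recent historical controls;
- a split presentation: "Efficacy results will be presented by dose level and AIS grade, and across all subjects as appropriate".

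The historical figures are in protocol 1.3.1: 21% at 24 weeks and 26% at 48 weeks after injury, for C4–C7 AIS-A injuries only. Section 9 sets the status of all of this: "All analyses will be descriptive in nature".

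**SAP.** Section 5.1 defines the Intent to Treat Population as injected subjects in Cohorts 2 to 5 and adds: "This population will be used for all efficacy analyses, and results will be presented for the overall, aggregated population". Sections 6.3.1 (UEMS), 6.3.2 (SCIM) and 6.3.5 (GRASSP) each repeat that the summary is for that population overall. Section 6.3.1 also lists a percentage with two or more motor levels gained on at least one side; it names no cohort, dose or AIS grade, so the rule in 5.1 governs. Section 5.5 rules out subgroup analyses, citing small sample size and design. In section 9.1 the five efficacy tables (14.2.1.1, 14.2.1.2.1, 14.2.1.2.2, 14.2.2 and 14.2.3) are all for the Intent to Treat Population. Historical controls are not mentioned.

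On precedence, SAP section 2 states that where the two differ, "the description in this document supersedes the descriptions in the statistical section of the protocol".

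**The concern.** Because the SAP takes precedence, the protocol's displays are dropped; they do not continue as a parallel plan. Four things change together: Cohort 1 leaves the efficacy tables, the AIS-A responder percentage disappears, the historical comparison disappears, and the dose and AIS-grade split is replaced by one pooled column. The SAP does not identify any of these as a departure from 9.3.2, and the general remark in 5.5 is the only reason offered.

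The secondary objective is change in neurological function. The only external yardstick the protocol gives for it is an AIS-A rate, and a figure that mixes AIS-A with AIS-B does not identify that rate. In a dose-escalation study, no motor, independence or hand-function table would show results by dose. The interim analysis in SAP 5.4 uses the same tables, so it would have the same gap.

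**Working it through.** **1. Denominators.** SAP 3.2.1 reports that "a total of 25 subjects were enrolled and received AST-OPC1 across the five cohorts", with counts of 3, 6, 6, 6 and 4. The sum 3 + 6 + 6 + 6 + 4 = 25 reproduces the stated total. Grade and dose by cohort come from the protocol synopsis.

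| Group | Cohorts | n |
|---|---|---|
| SAP efficacy set | 2–5 | 6 + 6 + 6 + 4 = 22 |
| AIS-A responder group of 9.3.2 | 2, 3 | 6 + 6 = 12 |
| AIS-B | 4, 5 | 6 + 4 = 10 |
| 1 × 10⁷ cells | 2, 4 | 6 + 6 = 12 |
| 2 × 10⁷ cells | 3, 5 | 6 + 4 = 10 |
| Left out of efficacy tables | 1 | 3 |

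**2. What a pooled count reveals about AIS-A.** Suppose k of the 22 gain at least two levels and all 22 are assessed. At most 10 of the k can be AIS-B, so the AIS-A count lies between max(0, k − 10) and min(12, k). No AIS-B response rate has to be assumed.

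- Example, k = 8 (8/22 = 36%): the AIS-A count can be anything from 0/12 to 8/12, or 0% to 67%.
- Against 21%: 2/12 = 16.7% is below and 3/12 = 25% is above. The position is undetermined when min(12, k) ≥ 3 and max(0, k − 10) ≤ 2, that is k = 3 to 12, or 13.6% to 54.5% pooled.
- Against 26%: 3/12 = 25% is below and 4/12 = 33.3% is above. It is undetermined when min(12, k) ≥ 4 and max(0, k − 10) ≤ 3, that is k = 4 to 13, or 18.2% to 59.1% pooled.

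**3. Precision of the restored row.** Exact (Clopper–Pearson) 95% intervals: 4/12 gives 9.9% to 65.1%; a single cohort at 2/6 gives 4.3% to 77.7%.

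**4. Timing against the benchmark.** The benchmark runs from injury and the visits run from injection. With dosing 21 to 42 days after injury, nominal Day 180 falls 201 to 222 days after injury (28.7 to 31.7 weeks, against 24), and nominal Day 365 falls 386 to 407 days after injury (55.1 to 58.1 weeks, against 48). The two are not aligned, and a footnote has to say so.

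**5. Whether small numbers explain the pooling.** Most SAP safety summaries are by cohort and overall: adverse events (6.2.2), laboratory tests (6.2.3), vital signs (6.2.5), physical examination (6.2.6) and neuropathic pain (6.2.8). SAP 4.3 lists neuropathic pain as an exploratory endpoint alongside SCIM and GRASSP. Cells of 3 to 6 were therefore acceptable there. Protocol 9.3 also foresaw small samples per dose and AIS grade, and its answer was to supplement the tabulations with subject narratives.

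**The case against.** The strongest case is that the SAP made an open choice within its authority. It claims precedence, states the pooling consistently and gives a reason in 5.5. No listed endpoint is lost: UEMS with its confidence interval, motor-level change and a pooled two-or-more-level percentage all remain. The protocol itself allows results across all subjects where appropriate, and its section 1.3.1 gives some ground for looking across AIS grades with SCIM and GRASSP. There is also some ground for treating Cohort 1 separately: its dose is 2 × 10⁶ / 1.2 × 10⁷ = one-sixth of the estimated human equivalent dose, and 9.3.2 leaves it out of the responder analysis. Subject listings cover everyone treated, so the AIS-A count can be made by hand from 12 people. The SAP plans no comparison of the pooled figure with 21% or 26%, and an AIS-A interval as wide as 10–65% would cover both benchmarks. Table shells are not in the documents, so the column layout is inferred.

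Much of this stands as a limit on the harm. It does not remove the gap. A hand count from listings is not a planned analysis. The protocol's allowance for pooled results adds to the split and does not replace it. The AIS-A responder percentage is planned without any qualifier. The reason in 5.5 did not prevent cohort columns in most safety tables (ECG, medical history and concomitant medications state no split). The missing shells leave little doubt, because SAP 5.1, 5.5, 6.3 and 9.1 all point the same way.

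**Conclusion.** The concern holds and should be fixed. Followed as written, the SAP leaves the protocol's AIS-A responder question, and its dose and AIS-grade presentation of efficacy, without any table. The pooled percentage cannot stand in for the AIS-A figure: over pooled results of 14–55% (for the 21% benchmark) or 18–59% (for 26%), it does not settle on which side of the benchmark the AIS-A rate lies.

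Those bounds assume that all 22 subjects are assessed at the visit. The size and direction of any difference between the pooled and AIS-A rates are unknown, and it is nil if the two grades respond equally. Since everything is descriptive, no test or error rate is affected.

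**What to change.** 1. In SAP 5.1, 5.5 and 6.3 and in Tables 14.2.1.1 to 14.2.3, add columns by cohort and by AIS grade (AIS-A Cohorts 2+3, AIS-B Cohorts 4+5). Show Cohort 1 descriptively and keep the pooled column.
2. Restore the row for AIS-A Cohorts 2+3 gaining at least two motor levels at Days 180 and 365, placed beside 21% and 26% as a descriptive comparison only. An exact 95% CI is a small addition: 9.3.2 asks for intervals on UEMS and motor level, not explicitly on this percentage.
3. Footnote the side rule (SAP 6.3.1 uses at least one side), the benchmark's timing from injury against visits timed from injection, and the benchmark's C4–C7 range.

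If the sponsor prefers pooled tables only, the SAP should say why it departs from 9.3.2, and the pooled percentage should not be compared with the AIS-A benchmark.

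The cost is SAP wording, extra columns and one row, all from data already collected. The downside is cells of 3 to 6 per cohort and 12 for the AIS-A row, with intervals as wide as those shown above.
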